Pain catastrophizing – Pain catastrophizing will be measured by the Pain Catastrophizing Scale (PCS).⁵³ The PCS is a 13-item self-report scale, with each item rated on a 5-point scale: 0 (Not at all) to 4 (all the time). It is broken into three subscales (magnification, rumination, and helplessness); results from the initial development and validation studies indicate that the PCS is a reliable and valid measurement tool for catastrophizing in clinical and non-clinical populations. PCS will be completed prior to and following completion of the intervention and at the 3- and 6-month follow ups to assess the durability of the intervention.

Depression and Anxiety - To measure symptoms of depression and anxiety, the PROMIS® (Patient-Reported Outcomes Measurement Information System) person-centered measures will be utilized.⁵⁴ Specifically, the 8-item PROMIS depression and anxiety short forms will be compared prior to and following completion of the intervention; to evaluate the stability of CBT skills, the PROMIS will also be administered at 3 and 6 months.

Potential confounders – Pre-existing medical comorbidities or post-operative complications may affect surgical outcomes with respect to pain severity and resolution. To account for the effects of these confounders, all medical comorbidities will be extracted from the EHR by the study coordinator prior to surgery and recorded in the study database. Also added to the study database will be any unanticipated adverse events following surgery, and with medical comorbidities, considered as moderators of the effects of the intervention on the development of CPSP.

Post-operative pain intensity – Severity of post-operative pain will be operationalized as (1) responses on a visual analogue pain scale (VAS) and (2) consumption of opioid analgesic medications during the first 72 hours following surgery. The VAS ranges from 0 (no pain) to 10 (worst pain imaginable), and pain scores are collected every 4 hours as part of routine practice. Pain ratings will be graphed over time and area under the curve calculated. Dose of opioid analgesics consumed during this period (24hr increments and total) will be abstracted from the electronic health record and converted into MEDD for analysis.

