Opioid taper: As a part of the intervention and with the guidance of their trained coach, one-half of the subjects will be encouraged to gradually taper their opioid use in the month prior to surgery. It is possible that in doing so, subjects may experience the uncomfortable symptoms associated with opioid withdrawal. To avoid the emergence of these, subjects will be instructed to taper their dose gradually (no more than 10%/week), and will be provided with information on how to self-manage these symptoms should they arise. In addition, subjects will be instructed to contact their coach should the symptoms become severe, to receive guidance on how to temporarily cease and then restart taper attempts. In that subjects will have been regular users of opioids for at least three months prior to study enrollment, they will have developed a certain degree of physiologic tolerance, offering protection against any respiratory depressant effects during a taper pause.

Breach of Confidentiality: Participation in this study may constitute a social risk to the participant in that others may learn that he or she has chronic pain and is taking opioid medications. Due to the sensitive nature of this information, privacy and confidentiality will be strictly maintained in all aspects of participation. Consent and data collection sessions will take place in private rooms where strict privacy is enforced and all staff are HIPAA certified.

Acute Anxiety or Depressive Symptoms: It is possible that the opioid taper for the intervention group, or the upcoming surgery for both groups may precipitate unanticipated symptoms of acute anxiety or depression. As described below, co-PI [name] is a licensed clinical psychologist with over 40 years' experience in treating patients with chronic pain, will be available to assess and intervene with patients who experience these distressing symptoms during the pre-operative period.

2. Benefits:

The potential benefit for both the participants and broader segments of society is to improve pain outcomes following a very common procedure, TKA, ideally decreasing the severity of post-operative pain experienced and

the development of CPSP. Development of an effective intervention to address the risk factors for poor pain outcomes following TKA can guide clinical practice based upon evidence.

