Precautions are in place to ensure the data is secure by using passwords and encryption, because the research involves web-based surveys.

Audio and/or video recordings will be transcribed and then destroyed to eliminate audible identification of subjects.

Other (specify):

5. Protected Health Information

Five types of protected health information will be collected, subject's name, telephone number, email address, medical record number, and date of birth. The first three are required to allow for the 3- and 6-month follow up, and the medical record number will enable us to extract data on post-operative pain and opioid use. Date of birth will be collected to verify age. These data will not be shared with persons not involved in the study, all of whom have completed HIPAA training.

6. Compensation:

Subjects will receive no compensation for participating in the study.

7. Data and Safety Monitoring:

The Penn Center for Substance Abuse Treatment (CSA) has a standing data and safety monitoring board (DSMB) which will be used for this study. The purpose of the DSMB and consistent with NIH guidelines is to

assure that the safety of subjects is protected while scientific goals are being met. Specifically, the CSA DSMB is charged with monitoring the safety of participants and the quality of data, as well as the appropriate termination of studies when significant benefits or risks have been uncovered or when it appears that a clinical trial cannot be concluded successfully.

All board members meet NIH requirements regarding background and experience, and none will have ethical conflicts including financial interest related to study outcome. Individuals invited to serve on the board disclose any potential conflicts in writing. The board meets every six months (unless more frequent meetings are deemed necessary) and is chaired by [name] Ph.D. a faculty member within the Department of Psychiatry at the University of Pennsylvania. Other members of the board include [name]. (senior statistician), [name]., [name], MSN, CRNP who are faculty members or staff of the Perelman School of Medicine at Penn. Issues related to recruitment, safety and efficacy, whether the study questions are being answered, conflict of interest, confidentiality, and ongoing study review (including AEs, SAEs, and regulatory issues) are assessed.

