Following each DSMB meeting, the designated member standing in for the Chair will make recommendations to Drs. [name] and [name] and a final report (edited by all Board members not in conflict with this project) will be prepared and submitted to NINR, the Penn IRB, and the FDA (if required) according to each body's reporting requirements. In addition, a Data Safety Monitoring Board report is issued to the NINR Project Officer with the annual progress report.

The DSMB will meet to review safety data every six months (unless more frequent meetings are deemed necessary). At least two weeks prior to each meeting, the investigative team will submit to the DSMB a DSMB Report detailing screening activities; reasons for screening failures; subject enrollment (actual vs. expected); sociodemographic characteristics of enrolled subjects; and subject disposition (including reasons for attrition). In addition, the number and nature (severity and relatedness to study procedures) of all adverse events will be described. Finally, a random or purposive sample (depending on DSMB request) of subject case report forms (CRFs) will be submitted with the DSMB Report, to enable assessment of compliance with IRB requirements, conformance with informed consent requirements, verification of source documents and investigator compliance.

In the event that a subject scores high on the depression scale, a licensed clinical psychologist (co-PI [name]) will be available to assess immediately any patient who exhibits extreme anxiety, depression or suicidal ideation on routine screening or during the preoperative period. All research and clinical staff will call his cell phone when a patient with significant anxiety, depression or suicidal ideation is encountered. All patients who acknowledge extreme anxiety, depression or suicidal ideation and intent will be contacted immediately by [name] and an appropriate treatment plan will be enacted.

8. Investigator's Risk/Benefit Assessment:

Based on the characteristics of the risks associated with study participation, and efforts in place to minimize these risks, the risks to subjects are considered reasonable in relation to the anticipated benefits to research participants and others.

INFORMED CONSENT:

1. Consent Process:

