The Study Coordinator/Coach, TBH, will devote 12 calendar months effort to the study over both years of the project. This individual will come to the project with experience in coordinating human subject clinical research studies and be responsible for enrolling subjects, scheduling study visits, all aspects of data collection, entering study data into REDCap, and engaging in ongoing communication with IRB, study setting and U Penn School of Medicine and Nursing, Department of Anesthesiology and Department of Orthopaedic Surgery. In addition, this individual will receive directed training and monitoring from Co-PI [name] to oversee delivery of the CBT and opioid tapering MI intervention. In this role, this individual will serve as a "coach" to the subjects, contacting them on a weekly basis prior to surgery, educating and motivating them to engage in preoperative opioid reduction.

Participants will be recruited from the nationally renowned Department of Orthopaedic Surgery at PPMC. Center surgeons perform approximately 1800 major TKAs per year, an estimated 20-30% of whom have been taking opioids for at least 3 months for the treatment of a chronic nonmalignant pain condition, resulting in a recruitment pool of 30 to 45 patients per month, providing an adequate source of the necessary 12-13 enrollments per month.

In addition, the facilities and resources are adequate to safely conduct the study. Situated within the Department of Psychiatry is the Center for Studies on Addiction (CSA), where Co-Principal Investigator [name] holds an appointment. A primary mission of the CSA is to continue to advance the cutting edge of knowledge on the nature of addiction and the best ways to treat this disorder. The CSA has, for the past 40 years, been an important

national and international resource for addictions research. The PI ([name]) has conducted large-scale studies on pain and opioid use disorders and suicide and has an established relationship at the primary recruitment site.

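### The DSMB is promised all adverse events, but the plan specifies no systematic way to collect opioid withdrawal before surgery, and event counts would not be comparable between arms

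*Combined protocol and SAP*

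**What the plan says.** **The risk.** Under Risk/Benefit Assessment, 1. Risks, the taper comes first: "one-half of the subjects will be encouraged to gradually taper their opioid use in the month prior to surgery". The section then foresees withdrawal: "It is possible that in doing so, subjects may experience the uncomfortable symptoms associated with opioid withdrawal". For symptoms that are troublesome, "subjects will be instructed to contact their coach should the symptoms become severe".

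**The promise.** Under Risk/Benefit Assessment, 7. Data and Safety Monitoring, the DSMB report is to be comprehensive: "the number and nature (severity and relatedness to study procedures) of all adverse events will be described". The board's remit includes ending a study when significant risks come to light.

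**The data item.** Under Methods, 1. Study Instruments (Potential confounders): "Also added to the study database will be any unanticipated adverse events following surgery". Together with comorbidities, these events are to be "considered as moderators of the effects of the intervention on the development of CPSP".

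**The contacts.** Under Resources Necessary for Human Research Protection, the coordinator acts as coach to the intervention arm, "contacting them on a weekly basis prior to surgery, educating and motivating them to engage in preoperative opioid reduction".

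**The concern.** A safety report can contain only what someone asked about or happened to hear. Here the harm most directly tied to the intervention is foreseen and arises before surgery. The one adverse-event item named for the database is limited to events that are not foreseen and that come after surgery. If no other collection is specified, the DSMB's view of the taper depends on what patients volunteer.

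Two things are at stake. The first is monitoring: a low withdrawal count could mean that the taper is well tolerated, or only that mild and moderate symptoms were never elicited. The second is what the trial passes on. The Statistical Analysis section says that the primary goal is reliable effect-size estimates for larger studies. A successor trial would also want tolerability figures, and ones based on unprompted reports in a single arm would be a weak basis for planning.

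**Working it through.** The plan gives no adverse-event figure to reproduce, so the check is mainly a comparison of texts.

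1. **Withdrawal against the database item.** The item sets two conditions: the event is unanticipated, and it follows surgery. Withdrawal during the taper is a listed risk and arises in the month before surgery. It meets neither condition.

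2. **The schedule** (Methods, 4. Administration of Surveys and/or Process). Its nine rows are BPI, MEDD, PDMP review, PCS, PROMIS, CBT use and satisfaction, 72-hour VAS, 72-hour MEDD and the CPSP checklist. None is for adverse events or withdrawal, at any time point.

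3. **The visit narrative** (Study Procedures, 1. Detailed Description), which sets out to cover every visit and contact.
   - Baseline: pain, opioid use, catastrophizing, depression and anxiety, evidence of opioid use disorder.
   - Pre-operative session: baseline assessments repeated, plus an interview about the intervention.
   - First 72 hours: pain and opioid use from the EHR, or from a diary after early discharge.
   - Calls at 3 and 6 months: CPSP checklist, BPI and opioid use where relevant, PCS, PROMIS.

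   No adverse-event question appears at any of them.

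4. **The taper window itself.** The coach teaches patients to recognise and manage withdrawal, and makes weekly contact to educate and motivate. Neither description says that the coach asks about symptoms or records them. A coach log cannot be presumed, because Methods, 2. Group Modifications gives the satisfaction survey as the sole difference in measures between the groups.

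5. **Inputs to the DSMB report.** The report is to give severity and relatedness. The documents contain no adverse-event definition, grading scale or relatedness procedure.

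6. **Comparability of arms.** Let *p* be the true risk of an event, *s* the probability that an event is recorded, and *n* the arm size. The expected recorded count is *n·p·s*. With equal *n*, the ratio of recorded counts is (*p*₁*s*₁)/(*p*₀*s*₀), which equals *p*₁/*p*₀ only if *s*₁ = *s*₀. One arm has weekly contact with a coach and the other has none before the pre-operative visit, so there is no reason to expect equal *s*.

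7. **What a zero count would mean.** With 75 treated patients and no recorded event, the exact one-sided 95% upper bound on the recorded rate is 1 − 0.05^(1/75) = 0.039, or 3.9%. With 83 it is 1 − 0.05^(1/83) = 0.035, or 3.5%. These bound *p·s*, not *p*. For 75 patients the bound on the true risk is 0.039/*s*. It is 3.9% only if every case is recorded (*s* = 1), and the documents give nothing from which to set *s*.

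**The case against.** The strongest reply is that the database sentence is not a safety rule. It stands under Potential confounders, in a paragraph that opens with comorbidities and post-operative complications, and it names a covariate for the CPSP analysis. A post-surgical limit suits that purpose. The safety text elsewhere is wider. The DSMB report has no limit on timing or expectedness, the board's remit is broad ("ongoing study review (including AEs, SAEs, and regulatory issues) are assessed"), and Methods, 5. Data Management has weekly reports to the investigators on health events. The coach who teaches withdrawal management is also the coordinator who enters the data, so anything the coach hears reaches the right person. The pre-operative interview asks treated patients about the taper and about burden. The DSMB section also mentions case report forms that are not reproduced, so it cannot be shown that no adverse-event form exists.

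Much of this stands. A reader might infer that the plan defines adverse events for the whole trial as unanticipated post-surgical events. It does not: a covariate rule and a wider safety report can both hold. A reader might also infer that the DSMB is bound to miss withdrawal. That does not follow either, because the report as worded would include any withdrawal that staff learn of.

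The reply does not supply a collection method. The DSMB, weekly-report and remit passages say what will be reported or reviewed, not how events are elicited. The interview covers one arm and concerns use and satisfaction, so it yields neither counts nor severity. Setting the covariate sentence aside does not help the plan, since no adverse-event collection would then be specified at all. The gap is specific to withdrawal and general pre-operative events. Acute anxiety and depression are partly covered by PROMIS at baseline and before surgery and by the psychologist pathway.

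**Conclusion.** The point holds as a gap between a promise and the means to keep it. The plan undertakes to report all adverse events with severity and relatedness, and names pre-operative withdrawal as a taper risk, but specifies no systematic route for collecting it. Followed as written, withdrawal that is not severe would probably be under-ascertained, and adverse-event counts could not be compared between arms.

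The group exposed is the intervention arm: 75 planned, 83 if recruited with the attrition allowance. How many cases would go unrecorded cannot be estimated, because the documents give neither a withdrawal rate nor a reporting rate. The conclusion assumes that the coach does not routinely ask about and record symptoms beyond what is described, and that no unreproduced form fills the gap. If either assumption is wrong, the remedy is to say so in the protocol. This should be changed before enrolment, but it does not affect the validity of the efficacy analysis.

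**What to change.** Reconcile Potential confounders, the data collection schedule, the Risks section and the Data and Safety Monitoring section:

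- Keep the post-surgical moderator variable as it is. State separately that all adverse events, anticipated or not, are recorded from consent to the 6-month contact in both arms, and say how severity and relatedness are assigned.
- Add an adverse-event row to the schedule. Ask the same short scripted question in both arms at the pre-operative visit and at the 3- and 6-month calls. For the first 72 hours, use EHR abstraction, or the existing diary after early discharge, since no patient interview is planned then.
- Make clear that controls attend the pre-operative session. Study Design has both groups giving data then, while Study Procedures describes the session for the experimental group only.
- Have the coach log withdrawal symptoms and taper pauses at the existing weekly contacts. Label these as intervention-arm-only data, keep them out of between-arm comparisons, and amend Group Modifications to match.

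The cost is one extra REDCap form, a few minutes per contact and a higher recorded event rate. Controls would be recalling about four weeks at the pre-operative visit, which is a limitation to state. Nothing here alters the taper or any clinical rule.

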As described above, internet-based CBT has proved effective for patients suffering lower joint chronic pain, however it has been primarily delivered in post-operative or primary care settings, not preoperatively to improve surgical pain outcomes. Evidence from bariatric surgery populations suggest that benefits associated with preoperative CBT include decreased problematic eating behaviors and affective distress following surgery (pain outcomes not examined).^{44,45} Much of the work in preoperative interventions for TKA focus on physical rehabilitation,⁴⁶ as opposed to targeting chronic pain symptoms, opioid therapy and distress, which may explain findings of only slight and short-term improvements in early postoperative pain and function.⁴⁷ Only two reports testing CBT-based interventions prior to TKA could be found in the literature (one feasibility trial⁴⁸ and one randomized clinical trial²¹), and both focused only on managing symptoms of distress (depression, anxiety, catastrophizing); neither considered the roles of preoperative pain, opioid consumption or post-operative pain severity in predicting longer term outcomes (pain, long-term opioid use, functionality).

CHARACTERISTICS OF THE STUDY POPULATION:

1. Target Population and Accrual:

A total of 150 male and female chronic pain patients on opioid therapy seeking total knee arthroscopy (TKA) at the Penn Presbyterian Medical Center will be included in the study sample, half of whom will be randomly assigned to receive the targeted computer-assisted CBT intervention beginning 4 weeks prior to their planned TKA surgery; as the control condition, the others will receive treatment-as-usual, consisting of a mandatory four-hour educational session.

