STUDY DESIGN:

A randomized clinical trial is proposed to evaluate the efficacy of the novel computer-assisted preoperative CBT/opioid sparing intervention to affect acute and chronic post-operative pain outcomes. Specifically, 150 male and female patients meeting study inclusion criteria and preparing to undergo TKA at the Penn Presbyterian Medical Center will be randomized to either receive the computer-assisted preoperative CBT intervention (n=75) or treatment-as-usual (control, n=75). The effectiveness of the intervention to address the preoperative risk factors for CPSP will be evaluated by comparing pain severity, opioid use, symptoms of depression, anxiety and pain catastrophizing before and following the 4-week pre-surgical period and compared within and across subjects. Post-operative pain severity will be abstracted from the electronic health record (EHR) and compared to post-operative pain severity ratings between the intervention and control groups. Similarly, group differences will be inspected for rates of CPSP at 3- and 6-months following surgery. In addition, due to the novelty of the CBT/opioid sparing intervention, brief (15-20min) qualitative interviews will be conducted with the participants who received it during the study visit immediately prior to surgery, to assess patient utilization, and satisfaction with the program in general, and the opioid taper component specifically; adherence is tracked by the PAINTrainer. Participants will be prompted to comment on the perceived ease of use, burden, helpfulness and quality of the CBT intervention.

A randomized clinical trial was designed because it provides the highest level of evidence and lowest risk for bias. The methods employed are predominantly quantitative, although a qualitative survey approach is used to assess subject satisfaction with the intervention. The project is designed, staffed and budgeted to be completed in 24 months. In consultation with consultants, [name] will train the study coordinator coach on delivering the opioid taper intervention during months 1-3, during which time study start-up activities will take place. Enrollment will begin month 3; at a rate of 12-13 enrollments per month, we anticipate having enrolled 166 subjects (n=150, assuming 10% attrition) by study month 15, providing adequate time for 3- and 6-month follow up, and dissemination activities.

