session before completing it and resume where they left off, and access program resources to manage goals and reminders, log practices, review progress in easy-to-read graphs, read about others' experiences using the skills, and share their own. In addition, they will have access to PAINTrainer for one-month post operatively to reinforce the basic CBT principles; the program also tracks participants' use. Although it is recommended to complete one session per week, in this application patients will be asked to complete 2 sessions per week for four weeks; the developers of the PAINTrainer (consultants [name] and [name]) note that the efficacy of flexible approaches, including shortening of the delivery schedule.

In addition to the PAINTrainer, we will integrate a motivational interviewing (MI) intervention delivered by a trained "coach" across the sessions about (1) the benefits of opioid tapering for post-operative pain control, (2) approaches for safely tapering, (3) identifying and managing withdrawal symptoms patients may experience. Co-PI [name] will provide scripted language and train the study coordinator to effectively deliver this education within the CBT context employing MI techniques, and monitor fidelity to the delivery at regular intervals over the course of the study. The content and tapering guidelines will be based upon the US Department of Veterans Affairs Pain Management Opioid Taper Decision Tool⁵⁵ which provides guidance on dose reduction schedules, over-the-counter medications to treat mild withdrawal symptoms, and resources to manage discomfort or distress. Patients will not be expected to taper completely off opioids during the intervention period, but up to 30% reduction in daily opioid dose is anticipated. For future testing, the MI intervention will be integrated into the platform virtual coach, however it is cost-prohibitive to do so in the current application.

Treatment as usual: Patients scheduled to undergo total joint arthroplasty at the study site are automatically enrolled in a mandatory 4-hour education class delivered by a nurse educator or physical therapist. Utilizing an in-person PowerPoint presentation format, patients are informed about pre-habilitation exercises to do prior to surgery; what to expect the day of surgery; the multimodal analgesia protocol used in the perioperative period; options for anesthesia and analgesia; and the expectation of physical therapy after surgery.

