For the second study objective, we expect that participants, who receive a MI intervention along with a validated computer-assisted CBT intervention for chronic pain (PAINTrainer) will demonstrate a significantly greater improvement in outcome variables from baseline vs those receiving usual care. The outcome variables will include change in the severity of pre-operative chronic pain, opioid use, and psychological risk factors (depression, anxiety, catastrophizing) for CPSP in the 4 weeks prior to surgery. Specifically, a mixed model analysis will be fit to the data using the Proc Mixed procedure in SAS.^{56,57} Residual modeling will be performed to check for significant violations in the distribution and constant variance assumptions and determine if variance stabilizing or normalizing transformations should be applied. Furthermore, sensitivity analyses will be run considering dichotomous versions of the outcome variables using multiple logistic regression.

For the third study objective, we will describe the effects of the CBT intervention on 72hr post-operative pain severity, and 3- and 6-month rates of CPSP in comparison to patients who received treatment-as-usual. A mixed effects model will be fit with Treatment Group (intervention and usual care) as a between subject factor and Time (72hr, month 3 and 6) as a categorical within-subjects factor. We will include as baseline covariates any factors that differ significantly between the groups at baseline or show significant relationships with the outcome.

Potential confounders (medical comorbidities, post-operative complications) will also be considered in the analysis.

The results from the mixed model analyses will be summarized by mean (SE) change from baseline for each group at each time point. The primary hypothesis will be evaluated at the alpha = 0.05 level and all contrasts/hypotheses will be considered exploratory and results will be interpreted with caution at alpha equal to 0.05 level. The primary goal will be to obtain reliable effect size estimates to inform larger studies. In that women are more likely to develop CPSP than men,^{8,16} sex as a biological variable will be considered as a possible moderator in all analyses.

RISK/BENEFIT ASSESSMENT:

1. Risks:

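### Post-operative complications and adverse events arise after randomisation; using them as confounders or moderators can bias the objective 3 estimates

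*Combined protocol and SAP*

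**What the plan says.** Three parts of the combined protocol and SAP bear on this.

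- **Timing** (Characteristics of the Study Population, item 1). Of the 150 patients, "half of whom will be randomly assigned to receive the targeted computer-assisted CBT intervention beginning 4 weeks prior to their planned TKA surgery". Allocation and treatment therefore both precede the operation.
- **Methods, 1. Study Instruments, paragraph on potential confounders.** It opens: "Pre-existing medical comorbidities or post-operative complications may affect surgical outcomes with respect to pain severity and resolution". It continues: "To account for the effects of these confounders, all medical comorbidities will be extracted from the EHR". It then adds to the database "any unanticipated adverse events following surgery, and with medical comorbidities, considered as moderators of the effects of the intervention", with CPSP as the outcome concerned. This one paragraph uses both labels, confounder and moderator.
- **Study Procedures, 5. Statistical Analysis.** The objective 3 model (72-hour pain, CPSP at 3 and 6 months) has this covariate rule: "We will include as baseline covariates any factors that differ significantly between the groups at baseline or show significant relationships with the outcome". A separate sentence follows: "Potential confounders (medical comorbidities, post-operative complications) will also be considered in the analysis".

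Nowhere is the use of complications confined to a sensitivity or mediation analysis. No main model without them is named, and nothing notes that treatment could affect them.

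**The concern.** A confounder of a randomised comparison would have to influence which arm a patient is in. An event after surgery cannot do that here. It can, however, be a consequence of the arm. The intervention is meant to change opioid dose ("up to 30% reduction in daily opioid dose is anticipated") and distress before the operation, so an effect on the peri-operative course is possible in either direction.

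If there is such an effect, conditioning on complications does two things. It removes whatever part of the treatment effect runs through them. It also compares patients who are no longer alike: those with a complication in one arm may differ in frailty from those with a complication in the other. Subgroups defined by adverse events after surgery have the same weakness, because randomisation does not protect them.

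What is at stake is the stated main purpose of the analysis, which is dependable effect sizes for planning larger trials. A shifted estimate would pass into the next trial's sample size. If the intervention raised complications, adjustment would also conceal part of a harm.

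**Working it through.** The plan gives no figure on this point to reproduce; its sample-size calculation does not depend on it. The check is a reading of the timing, then an illustration of how the bias behaves.

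**Step 1: order of events.** Randomisation, four weeks of intervention, surgery, complications and adverse events, then CPSP at 3 and 6 months. Pre-existing comorbidities come before this sequence and are legitimate covariates or moderators. Complications and events after surgery are not.

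**Step 2: inputs, all assumed.**

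- Direct effect of the intervention on pain: −0.70 points. This is close to the pre-post improvement in the sample-size paragraph (0.145 × 4.82 = 0.70), but that is a within-group figure for pre-operative pain, so it serves only as a scale.
- Each complication adds 1.0 point of pain.
- An unmeasured frailty factor adds 1.0 point of pain per SD and 1.0 to the log-odds of a complication per SD.
- Residual SD 1.6 points.
- Complication rates p(control) and p(CBT) are varied.

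**Step 3: formulas.**

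- Total effect = −0.70 + 1.0 × [p(CBT) − p(control)].
- Adjusted effect = total effect − γ × [p(CBT) − p(control)], where γ is the coefficient of complication in a linear model with arm and complication. Here γ is 1.0 plus the frailty gap, within an arm, between patients with and without a complication. Large-sample simulation gives γ of about 1.86.

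**Step 4: results.**

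| Complications, control vs CBT | Total effect | Adjusted effect | Change |
|---|---|---|---|
| 24% vs 24% | −0.70 | −0.70 | none |
| 24% vs 21% | −0.70 − 0.03 = −0.73 | −0.73 + 1.86 × 0.03 = −0.67 | 0.056 / 0.73 = about 8% too small |
| 24% vs 13% | −0.70 − 0.11 = −0.81 | −0.81 + 1.86 × 0.11 = −0.61 | 0.205 / 0.81 = 25% too small |
| 13% vs 24% | −0.70 + 0.11 = −0.59 | −0.59 − 1.86 × 0.11 = −0.79 | 0.205 / 0.59 = about 35% too large |

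Direct simulation of the four cases agrees with the adjusted column to within 0.01.

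**Step 5: if frailty were fully measured and adjusted for.** Then γ = 1.0, and at 24% vs 13% the adjusted effect is −0.81 + 0.11 = −0.70. That is the direct effect, still not the total effect.

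**Step 6: a second set of assumptions.** Take a direct effect of −0.33 SD, 20% complications in controls, 0.5 SD of pain per complication, and frailty raising the complication log-odds by 0 to 1 per SD. If the intervention lowers the rate by 5 to 10 percentage points, adjustment hides 7% to 22% of the benefit. If it raises the rate by 5 to 10 points, adjustment overstates benefit by 8% to 30%. With equal rates the two estimates agree within 0.001 SD.

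Both illustrations use a continuous pain score. Neither puts a number on the bias for CPSP as a yes/no outcome.

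**The case against.** **The text is loose.** The Statistical Analysis section says only that complications will be considered and gives no model term. The formal covariate rule just before it is restricted to baseline factors. Under Study Instruments, the action tied to accounting for confounders is the extraction of comorbidities. This stands in part: a reader might infer that adjustment for complications is a settled plan, and the documents do not go that far. But complications are named as confounders in both places, and the sentence adds them beyond the baseline rule. Adjustment is the natural reading, and nothing excludes it.

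**Bias is not certain.** This stands. It needs the intervention to change complication rates. The background section ties opioid use and distress to post-operative pain and CPSP, not to complications. The 24% versus 13% case assumes a cut of over 40%, for which the documents offer no support.

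**Frailty may be partly captured.** Comorbidities are also to be considered, which may reduce the frailty component. That is fair, but Step 5 shows that the total effect is still not recovered.

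**The shift is small beside sampling error.** With 75 per arm and an SD of about 2.0 in this illustration, the standard error is √(2 × 2.0² / 75) = 0.33, larger than the 0.20 shift. That is correct, but bias does not average out, and it costs nothing to avoid.

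**The analysis is exploratory.** The sample-size paragraph says so for CPSP. That lowers the stakes for inference but does not make a biased effect size a better planning figure.

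**Conclusion.** The point holds in conditional form. Post-operative complications, and adverse events after surgery, are post-randomisation variables. Treating them as confounders or moderators can bias the objective 3 estimates if the intervention alters their frequency. The documents give no complication rates, so neither direction nor size can be stated. The illustrative range runs from no bias, through 8% and 25% attenuation, to about 35% overstatement, and rests entirely on the assumed inputs.

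Three stronger readings are not supported:

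- That the estimates will be biased, and towards no effect. With equal rates there is no bias, and with more complications under CBT the benefit is overstated.
- That both roles apply to both outcomes. The moderator role is stated for CPSP only; for 72-hour pain the issue is the confounder wording.
- That the pre-operative results are compromised. Objective 2 concerns changes over the four weeks before surgery, including chronic pain severity, which the sample-size paragraph names as the primary outcome variable. Events after surgery have no place in that analysis.

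The change is worth making before analysis, as a modest correction.

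**What to change.** Change two sentences.

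- **Study Instruments, potential confounders:** keep pre-existing comorbidities as covariates or moderators. State that post-operative complications and adverse events after surgery are recorded and reported by arm as outcomes.
- **Statistical Analysis, objective 3:** state that covariates and moderators in the main models are limited to variables fixed before randomisation. Any analysis that conditions on complications or post-surgical adverse events goes in a separately labelled supplementary or mediation analysis, with its assumptions stated.

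The data can still be collected and examined; only their place in the main models changes. The cost is two sentences, with no new data and no change to the sample size.
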